- 1.11. Planning target volume (PTV) margins will be based upon the risk and predicted magnitude of extracapsular extension, as most recently reported by Chao, KK, et al, detailed in sections 6.1.2 − 6.1.4 of this protocol document. Briefly, for classic "favorable" prognosis patients (PSA≤10ng/ml, T-stage <= T2a and Gleason score ≤ 6), a radial margin of 2mm will be added around the prostate to create the planning target volume. The radial margin will be increased to 5 mm posterolaterally for the "intermediate prognosis" and positive perineural invasion cases, to account for their increased risk and potential radial distance of extracapsular extension from the prostate, which typically occurs along the neurovascular bundle. Proximal seminal vesicle coverage will be added for intermediate risk patients or those with prostate base involvement as detailed in section 6.1.1 of this document. In

all cases, where the outer surface of the rectum abuts the posterior surface of the prostate, the PTV margin in that area will be reduced to zero.

- 1.12. As most patients with low and intermediate risk prostate cancers survive at least 10 years after intervention, the morbidity associated with therapy for early stage prostate cancer is a crucial factor of patient outcome. Although traditional, physician-reported toxicity data are a useful component for evaluating treatment-related morbidity, it has been shown that patient-report data (collected via standardized questionnaires) are more sensitive than physician reports to the full severity and broad range of therapy effects on patient Health-Related Quality of Life (HRQOL), particularly among men with prostate cancer.¹³
- 1.13. The feasibility of CyberKnife for treating localized prostate cancer was first described by King at Stanford University. Their phase I protocol delivered 36.25Gy in 5 fractions of 7.25Gy. In a recent report of acute and 18-month late toxicity in 26 "low-risk" patients, no patient experienced grade 3 or 4 acute or late toxicity, and only one patient experienced a grade 2 late morbidity (urethral stricture). Toxicity was less than that reported in MD Anderson's external beam dose escalation trial. Mean PSA 18 months after treatment was 0.22ng/m¹⁴.

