- 1.14. Another potential benefit of CyberKnife radiosurgery relative to HDR brachytherapy is better preservation of potency, even if the radiation distribution is essentially identical between these modalities. This is so because needle trauma has been identified as a potentially significant contributory factor to erectile dysfunction with brachytherapy, including HDR-based monotherapy technique, presumably due to direct physical injury to the neurovascular bundle and/or bulb of the penis, particularly when greater than 13 needle insertions are performed.¹⁵ By comparison, CyberKnife radiosurgery is noninvasive, and so removes this particular erectile dysfunction risk factor.
- 1.15. To confirm our hypothesis that CyberKnife radiosurgery may be made to resemble a "noninvasive HDR dosimetry delivery system," in addition to simply creating equivalent dosimetry, it is necessary to show clinical equivalence both in terms of efficacy and toxicity.

Table 1. 5-Year bDFS Outcomes for HDR-Monotherapy for Prostate Cancer

HDR Details	Institution	# pts	Medianf/u yrs	Phoenix	ASTRO
6-7.25 Gy x 6	CA Endocurie ¹⁸	117	3.3		97%
9.5 Gy x 4	Beaumont ¹⁹	95	4.2		98%
7.5 Gy x 6	Texas Tech ²⁰	145	5		90%
6.5 Gy x 6	Gamma West – Fav. (SLC) ²¹	209	1.2	96%*	99%*
	Gamma West – Int. 21	119	1.2	89%*	89%*
6 Gy x 8-9	Osaka (Japan) ²²	111	2.25		70%†
	Totals	796	2.4		90%

^{*3} year result; Projecting constant failure rate in this series to 5 years yields 98% and 82% ASTROdefinition PSA DFS for favorable and intermediate risk cases, respectively. †Predominantly unfavorable prognosis cases in this series; 5 year local control is 97%.

Based on the data provided in the reports summarized above, and adding a PSA DFS degradation factor to the Gamma West series to compensate for their short median follow-up, the average calculated 5 year HDR monotherapy ASTRO-based PSA DFS is 98% for favorable prognosis, 82% for intermediate prognosis and 59% for unfavorable prognosis cases. There are too few Phoenix-based PSA DFS results to project a meaningful Phoenix-based HDR monotherapy PSA DFS efficacy result.

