It is anticipated that the case mix in this study will be approximately 70% low risk/ 30% intermediate prognosis cases, leading to a predicted CyberKnife monotherapy 94% 5 year PSA DFS rate, with a potential range of 82% (0% favorable or low risk prognosis cases accrued) to 98% (100% favorable cases accrued). If the protocol case mix deviates from these percentages, then the protocol DFS rate required to successfully test the primary efficacy hypothesis detailed in Section 2.0 may need to be adjusted accordingly.

Table 2. Toxicity review for HDR-Monotherapy for Prostate Cancer

				>= Gd 3 toxicity	•	
HDR Details	Institution	# pts	Median f/u	Total (%)	GI (%)	GU (%)
6-7.25Gy x 6	CA Endocurie ¹⁸	117	3.3	3	0	3
9.5Gy x 4	Beaumont ¹⁹	95	4.2	8	0	8
7.5Gy x 6	Texas Tech ²⁰	145	5	5-8*	1	4 – 7*
6.5Gy x 6	Gamma West (SLC) ²¹	328	1.2	1	0	1
6Gy x 8-9	Osaka (Japan) ²²	111	2.25	7	1	6
	Totals	796	2.4	6	0 -1	5

^{*3%} acute and 4% chronic grade 3 GU toxicity – It is unclear to what degree acute and chronic grade 3 GU toxicity populations overlap in this study.

Due to short median follow-up, the incidence of >= grade 3 late toxicity is likely underestimated. We project that the incidence of late toxicity will increase by approximately 50% when all data reach 5 years maturity, yielding a projected cumulative 5 year HDR monotherapy grade 3 toxicity incidence of 9% (7-8% GU; 1-2% GI). In this study, biochemical disease-free survival (ASTRO and Phoenix definition), freedom from local recurrence, freedom from distant relapse, clinical disease-free survival, disease-specific survival and overall survival will be recorded. The incidence of grade 3 or higher toxicity and the effect of CyberKnife® radiosurgery on bladder, bowel, and sexual function will be followed and monitored using standardized, patient self-administered questionnaires and compared with results published in peer-reviewed literature for other prostate cancer therapeutic modalities. 17

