We chose N large enough to test the null hypothesis against the alternative hypothesis with power equal to 80% at the one-sided 5% significance level.

Let Z_u denote the upper u-th percentile of the standard normal distribution. Hence $Z_{.05} = 1.645$ corresponding to the one-sided 5% level of significance and $Z_{.20} = 0.84$ corresponds to 80% power. Then the sample size is determined by Formula 1:

$$N = \frac{\left[z_{\beta}\sqrt{\pi_{1}(1-\pi_{1})} + z_{\alpha}\sqrt{\pi_{0}(1-\pi_{0})}\right]^{2}}{\left[\pi_{1} - \pi_{0}\right]^{2}}, \text{ where}$$

 π_1 is the expected proportion of CyberKnife treated patients bDFS at 5 years if the alternative hypothesis is true; the bDFS rate is then expected to equal or exceed 0.94. For purposes of sample size estimation, we require 80% power if $\pi_1 \geq 0.945$. π_0 is the expected lower limit of the 95% confidence interval for π and is set equal to 0.90. Then N= 232. Allowing 8% sample size degradation for lost to follow-up, the sample size must be increased to 232/.92 = 253 subjects.

Primary Safety Objective

The primary safety objective is to establish with 95% confidence that the percentage of CyberKnife treated patients experiencing \geq Grade 3 toxicity is not more than 5% higher than the approximately 9% 5-year rate extrapolated from Table 2, Section 1.15.

With N=232 CyberKnife treated subjects, if the observed \geq Grade 3 toxicity rate equals 9%, then with 95% confidence the "true" rate \leq 12.6%. Since the difference between 12.6% and 9% is less than 5%, the sample size of 232 subjects is more than large enough to meet the primary safety objective.

11.3.1 ACCRUAL RATE: the initial three months while institutions are obtaining IRB approval, therefore we do not expect to meet the targeted monthly accrual rate until after the first three months. The estimated accrual rate is 2 patients per study site per month. Expectations of 5 treating study sites assumes an accrual period of approximately 29 months total.

11.4STATISTICAL METHODS

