"Survival" is variously defined in Sections 1.1.5, 2.0. Periodically over the extended follow-up period, Kaplan-Meier "survival" curves will be calculated (examples: at 6 months, yearly, 5 years, at end of patient follow-up). From the Kaplan-Meier curve, descriptive statistics will be calculated including estimates of survival rates and mean and quartile survival times.

5.Work Effort

At each site and for each patient, time spent actively involved with planning and treatment shall be recorded for all member of the treatment team (therapist, physicist, radiation oncologist, and urologist). The required on-site supervisory time will also be recorded. Average times will be recorded. Time spent by team members will be compared with other outcomes (e.g. experience level of team member, patient enrollment, treatment planning/delivery QA outcomes, toxicity, bDFS and QOL outcomes) and correlations determined.

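### Section 11.4.2 plans mean and quartile survival times with no truncation time; for whole-cohort bDFS no quartile is expected within 10 years, and the mean would mainly reflect length of follow-up

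*Combined protocol and SAP*

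**What the plan says.** Section 11.4.2, item 4 (Survival) plans Kaplan-Meier curves, recalculated periodically over extended follow-up ("examples: at 6 months, yearly, 5 years, at end of patient follow-up"). It then says: "From the Kaplan-Meier curve, descriptive statistics will be calculated including estimates of survival rates and mean and quartile survival times". No truncation time is given for the mean, and nothing is said about a quartile that the curve does not reach.

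Item 4 takes its definitions of survival from Sections 1.1.5 and 2.0. There is no Section 1.1.5; I read it as 1.15. Both 1.15 and 2.0 include bDFS as well as clinical disease-free, disease-specific and overall survival.

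On the expected level of the curves:
- Section 11.3, for bDFS under the alternative: "the bDFS rate is then expected to equal or exceed 0.94". The sample size itself uses 0.945, against a null of 0.90.
- Section 1.15, from the HDR literature: "PSA DFS is 98% for favorable prognosis, 82% for intermediate prognosis and 59% for unfavorable prognosis cases", with an expected case mix of "approximately 70% low risk/ 30% intermediate prognosis cases".
- Section 1.12, the only statement on long-term overall survival: "As most patients with low and intermediate risk prostate cancers survive at least 10 years after intervention".
- Section 2: follow-up runs to 10 years.

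**The concern.** A quartile of survival time can be read from a Kaplan-Meier curve only once the curve has fallen to 75%, 50% or 25%. An unrestricted mean needs the curve to reach zero. When most men are still event-free at their last visit, what is reported as a mean is the area under the curve up to wherever it is cut. If bDFS is as good as the plan expects, that area is close to the cut-off itself.

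Successive reports could then show a mean bDFS time that rises from one analysis to the next only because men have been followed longer. Two analysts with the same data could also report different means at one analysis, because the plan does not say where to cut.

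**Working it through.** **The plan's own figures.** Formula 1 in Section 11.3 with π0 = 0.90, π1 = 0.945, z = 1.645 and 0.84:

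N = [0.84·√(0.945·0.055) + 1.645·√(0.90·0.10)]² / 0.045² = 231.7, so 232; 232/0.92 = 252.2, so 253. Both reproduce.

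The case mix gives 0.70·98% + 0.30·82% = 93.2%, slightly under the stated 94%. The difference does not affect what follows.

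**Assumption.** Constant failure rate, h = −ln(S5)/5, where S5 is 5-year bDFS. The plan makes the same kind of projection under Table 1.

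**Quartiles of whole-cohort bDFS.** The curve reaches 75% at t = ln(4/3)/h. At 94%, h = −ln(0.94)/5 = 0.01238 per year, and t = 0.2877/0.01238 = 23.2 years.

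| 5-year bDFS | bDFS at 10 years | Time to 75% (years) |
|---|---|---|
| 90% (null) | 81% | 13.7 |
| 93.2% | 87% | 20.4 |
| 94% | 88% | 23.2 |
| 94.5% | 89% | 25.4 |
| 98% | 96% | 71 |

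A 70/30 mixture of 98% and 82% gives 87.4% at 10 years and reaches 75% at 24.1 years. At 94% the median would come at 56 years.

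How far would the constant-rate assumption have to fail? To fall from 94% at 5 years to 75% at 10, the rate in the second five years would have to be ln(0.94/0.75)/5 = 0.0452 per year, about 3.6 times the 0.01238 implied for the first five.

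**Mean of whole-cohort bDFS.** The area under the curve to T is (1 − e^(−hT))/h. At 94%:
- T = 5: 4.85 years, 97% of the cut-off
- T = 10: 9.41 years, 94% of the cut-off

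The 5-year result hardly depends on the assumption. A curve that never rises and stands at 94% at 5 years has an area between 0.94·5 = 4.70 and 5.00 years.

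Moving 5-year bDFS from 90% to 98% moves the 5-year area only from 4.75 to 4.95 years. Moving the cut from 5 to 10 years at 94% moves it by 9.41 − 4.85 = 4.56 years. Follow-up therefore dominates the figure.

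The cut also matters within one analysis. Section 11.3.1 expects about 29 months of accrual. When the last man reaches 5 years, the first has 5 + 29/12 = 7.4 years. The same curve gives 4.85 years cut at 5 and about 7.1 years run to the longest follow-up.

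**Other endpoints.** Reaching 75% by 10 years needs a total event rate of at least ln(4/3)/10 = 2.88% a year.
- Intermediate-risk men, at 82% at 5 years: h = 0.0397, and bDFS reaches 75% at 7.2 years, inside the follow-up period.
- Overall survival, and disease-free survival counting any death (Section 9.4.3.2): the plan gives no expected rates. The death rates below are my assumptions; for disease-free survival they are added to the 94% bDFS rate.

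| Assumed deaths per year | DFS including death reaches 75% (years) | OS reaches 75% (years) |
|---|---|---|
| 1% | 12.9 | 28.8 |
| 2% | 8.9 | 14.4 |
| 3% | 6.8 | 9.6 |
| 4% | 5.5 | 7.2 |

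**The case against.** The strongest reply is that item 4 sits under secondary objectives, whereas bDFS is the primary endpoint with its own fixed-time confidence bound in 11.4.1. The 94% belongs to bDFS alone, so it says nothing about the other curves. This stands in part. The level of the other curves is not known from the plan, and a reader might infer that no quartile exists for any of them. The documents do not support that: a first quartile could fall within 10 years for disease-free survival including death, for overall survival, or for intermediate-risk men. But item 4 takes its definitions from sections that include bDFS, so bDFS is within its scope. For overall survival, Section 1.12 puts the 10-year curve above 50%, so its unrestricted mean is not estimable either.

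A second reply is that much of the remedy is already there. The same sentence plans survival rates, which remain estimable, and an unreached quartile is ordinarily reported as such. This also stands, and it limits the point to the mean, its missing horizon, and the wording on quartiles.

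Two further inferences should be resisted. One is that the reported mean understates a true mean bDFS of about 81 years (1/0.01238). That figure extrapolates a constant rate over decades and is no meaningful target in these men. The other is that comparisons with the HDR series or between risk groups would be distorted. Section 2 compares bDFS rates with published rates, and nothing in the plan compares mean times.

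**Conclusion.** The point holds for whole-cohort bDFS. At the plan's expected rate no quartile is expected within the 10 years of follow-up, and this remains so at the null rate. The unrestricted mean is not estimable, and the area that would stand in for it is about 94–97% of the cut-off. The quartile result rests on a roughly constant failure rate, and a more than threefold late rise would be needed to overturn it. The result for the mean at 5 years needs only the 94%. For overall survival the mean fails if, as the plan says, most men survive at least 10 years.

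The consequence is minor. These are descriptive secondary summaries; the efficacy criterion, the safety criterion, the interim boundary and the toxicity stopping rule do not use them.

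**What to change.** In Section 11.4.2, item 4, replace the sentence on mean and quartile times with one that specifies:
- Kaplan-Meier survival rates at the fixed times already planned, each with a 95% confidence interval;
- restricted mean survival time with its confidence interval, to 5 years at the primary analysis and to 10 years at the end of follow-up;
- a quartile only where the curve reaches that level, and otherwise *not reached*.

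This is one sentence and a standard software option, with no new data and no change to conduct. The one drawback is that a restricted mean can be read correctly only with its horizon beside it, so every table must state the horizon.

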12. DATA SAFETY AND MONITORING

- 12.1. Clinical information from the subjects will be recorded onto Case Report Forms and subsequently transferred into a computer database in a secure file at a reputable Clinical Research Organization that is experienced and operates in accordance with the applicable regulatory and HIPAA guidelines.
- 12.2. Accuray's clinical monitor will periodically analyze data and initial outcomes from SRS treatment in order to monitor for any information of clinical concern. Additionally, as warranted, safety information will be submitted by one of the lead site's investigators and/or Accuray's clinical monitor to Accuray's medical monitor.
- 12.3. INDEPENDENT DATA SAFETY MONITORING BOARD: An independent Data Safety Monitoring Board (DSMB) will act as an advisory board to monitor patient safety and evaluate the efficacy of CyberKnife Stereotactic Radiosurgery for treating low and intermediate risk prostate cancer. The DSMB will conduct an independent objective review of the data to maximize the benefit to the trial participants. The DSMB will consist of 3 clinicians who are experts in or representatives of the fields of radiation oncology, stereotactic radiosurgery, urology, clinical trial methodology, and biostatistics. Membership will consist of persons completely independent of the investigators who have no financial, scientific or conflict of interest with the trial. Meetings of the DSMB will be held 4 times a year, with one annual meeting taking place face to face and the remaining meetings occurring via teleconference. The first board meeting will meet prior to initiation of the study to

discuss the protocol and establish guidelines to monitor the study. The remaining quarterly meetings will be conducted via teleconference. The DSMB will monitor and evaluate all adverse events of all grades to establish relationship to the study procedures. Based on the review of toxicities summary the board will make recommendations to either continue, modify or terminate the study. After each meeting the board will provide the PI and Accuray with a written report concerning findings for the trial as a whole related to cumulative toxicities observed and any relevant recommendations related to continuing, changing, or terminating the trial. Information on cumulative toxicities and relevant recommendations will also be provided by Accuray to the rest of the participating sites to be shared with their IRBs.

- 12.4. Adverse Events: An unanticipated adverse effect is defined by the FDA as any serious adverse effect on health or safety or any life-threatening problem or death caused by, or associated with, a device, if that effect, problem, or death was not previously identified in nature, severity, or degree of incidence in the protocol (including a supplementary plan), or any other unanticipated serious problem with a device that relates to the rights, safety, or welfare of subjects. Should any unanticipated adverse device effects occur during the course of the study, the clinical monitor will ensure that they are documented by the investigator and reported to the sponsor and the reviewing Institutional Review Board (IRB) as soon as possible, but no later than ten working days after the investigator first learns of the effect(s). The report regarding any unanticipated adverse device effect also will be provided to all other IRBs for the sites at which this clinical evaluation is being conducted. The clinical monitor, on behalf of the sponsor, will work with one of the lead site's investigators and Accuray's medical monitor to conduct an evaluation of such effects. Following this evaluation, if the determination is made that an unanticipated adverse effect presents an unreasonable risk to subjects, the clinical evaluation will be paused, if deemed appropriate (to enable further investigation) or terminated as soon as possible. Termination shall occur no later than five working days after the sponsor makes the determination and no later than 15 working days after the sponsor receives notice of the unanticipated adverse device effect. In the event of termination, IRB approval will be obtained prior to resuming the clinical evaluation.
- 12.5. Below are criteria for early termination of the trial (through 25%,50% and 75% enrollment of 232 patients) should an excessive number of patients experience ≥ Grade 3 gastrointestinal and genitourinary toxicity. This depends upon the number so far enrolled and a criterion that identifies too high a rate. The stopping criteria differ after 58, 116 and 174 patients have been enrolled .Consistent with Section 1.1.5, 2.0 we define an observed ≥ Grade 3 gastrointestinal and genitourinary toxicity rate of over 14% as too high. The statistical requirement is that for up to "m" patients enrolled, the number of observed cases with ≥ Grade 3 toxicity must be few enough so that there is a 95% chance that the "true" rate does not exceed 14%.

≥ Grade 3 toxicity Stopping Criteria				
Participants to	Stop study if the number of patients with grade 3-5 toxicity			
be enrolled: 253	equals or exceeds:			
	Enrollment 1-58: 4 Events			
	Enrollment 1-116: 10 Events			
	Enrollment 1-178: 17 Events			

Page 27 of 52

Regulatory Reporting: Any reports regarding safety issues and potential safety issues will also be provided to Accuray's Regulatory Affairs Department. Such reports will be evaluated and reported to the FDA and all applicable regulatory agencies, as deemed required.

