- 6.2. PATIENT REGISTRATION: Patients may be registered only after all eligibility criteria are met: see Eligibility Checklist above, and Inclusion Criteria and Exclusion Criteria CRFs (Case Report Forms). After the patient signs the Consent Form the patient is enrolled in the study, and scheduled for treatment. The pre-treatment CRFs are then filled out by the investigator and/or research assistant. This data is retained in the patient's chart and in research office. The date of registration shall be the date the consent was signed. Fiducials must be placed within 60 days, and the first fraction of radiosurgery must be administered within 90 days of registrations.

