 - 8.3.2.4.1. For patients chosen for post-treatment review, the study Monitor will notify the treating site no sooner than 1 day, but no later than 7 days, after completion of treatment. Within one week, the treating site will deliver to the PI site: 1) Deidentified copy of the treatment planning data sets (including fused primary and secondary imaging studies, contour sets, and isodose distributions/DVHs), 2) Copies of the Pre-treatment Planning Preparation form, CyberKnife Treatment Planning form, and Treatment Plan QA form, 3) CyberKnife Treatment form, and screen captures documenting treatment delivery for all fractions. These will be reviewed by the PI and Physics chair within one week, with feedback given to the submitting site as needed.

8.3.3. EVALUATED STRUCTURES:

- 8.3.3.1.CTV: The Clinical Treatment Volume (CTV)
 - 8.3.3.1.1. LOW-RISK PATIENTS: (CS T1b-T2a, PSA 10, Gleason score 6): The CTV is the pre-registered MRI defined prostate volume, unless MRI-based imaging is medically contraindicated or judged inaccurate by the investigator (see

П

section 8.3.3.1.2.), in which case the CT may be used to define the CTV. Additionally, at the discretion of the investigator, some or all of the adjacent seminal vesicle volume may be included in the CTV for any of the following reasons: prostate base involvement by any criteria, perineural invasion, or equivocal MRI evidence of seminal vesicle invasion in a patient with no other clinical or pathological evidence for seminal vesicle invasion. In the event that the planning MRI reveals evidence for direct extracapsular invasion (Stage T3a) or seminal vesicle invasion (Stage T3b) that the investigator believes to be a true positive result, the patient will be withdrawn from the protocol and treated by an alternate method off protocol.

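### Section 12.5's toxicity stopping table prints 178 where 174 belongs and sits beside a conflicting threshold sentence; it also counts men from consent, so passing a milestone does not give the stated 95% confidence

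*Combined protocol and SAP*

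**What the plan says.** Section 12.5 sets early-termination checks at 25%, 50% and 75% of 232 patients and states: "The stopping criteria differ after 58, 116 and 174 patients have been enrolled". It then gives two descriptions of what is unacceptable.

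- It defines an observed "Grade 3 gastrointestinal and genitourinary toxicity rate of over 14% as too high".
- It then states the statistical requirement: the number of cases "must be few enough so that there is a 95% chance that the" true rate is no higher than 14%.

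The table stops the study at 4 events for enrolment 1-58 and 10 events for enrolment 1-116. Its last row reads "Enrollment 1-178: 17 Events".

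The rule depends on the number enrolled. Section 6.2 fixes when that happens: "After the patient signs the Consent Form the patient is enrolled in the study". It also allows a delay: "the first fraction of radiosurgery must be administered within 90 days of registrations". Under 8.3.3.1.1 and 8.3.3.1.2, if the planning MRI shows T3 disease that the investigator believes, "the patient will be withdrawn from the protocol and treated by an alternate method off protocol".

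The 14% is the 9% five-year literature rate plus the 5-point margin (Sections 1.15, 11.3 and 11.4.1). Section 12.5 states no follow-up window.

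**The concern.** A stopping rule should be readable in only one way, and this one is not. The third row disagrees with the text above it. The observed-rate sentence, taken literally, describes a far looser rule than the table.

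The third problem affects meaning more than wording. The 95% statement treats every man in the denominator as having been treated and fully observed. On the day the 58th man consents, some have had no radiation and others have had it only recently. A low count at that moment says less about a five-year rate than the text claims. The stake is a safety board, or a later report, treating a passed milestone as statistical evidence that it is not.

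**Working it through.** **Inputs.** Milestones: 0.25, 0.50 and 0.75 × 232 = 58, 116 and 174 (12.5). Threshold 14%, one-sided 95% (12.5). Accrual: "The estimated accrual rate is 2 patients per study site per month", with 5 sites expected (11.3.1), so 10 per month. Consent-to-treatment lag: up to 90 days (6.2). The lags actually taken are not in the documents, so 45 days and 90 days are shown as assumptions.

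**1. Reproducing the table.** Stop at the smallest x for which P(X ≤ x | n, 0.14) exceeds 0.05. Equivalently, stop when the exact upper limit U, the 0.95 quantile of Beta(x+1, n−x), exceeds 14%.

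| n | Largest passing count | P at 14% | U | Next count | P at 14% | U |
|---|---|---|---|---|---|---|
| 58 | 3 | 0.030 | 12.8% | 4 | 0.077 | 15.1% |
| 116 | 9 | 0.029 | 13.1% | 10 | 0.056 | 14.2% |
| 174 | 16 | 0.038 | 13.6% | 17 | 0.062 | 14.3% |
| 178 | 17 | 0.049 | 13.98% | 18 | – | above 14% |

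The printed 4, 10 and 17 are right for 58, 116 and 174. At 178, 17 events still pass and the boundary is 18. So the misprint is the 178 and not the 17.

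**2. The observed-rate sentence.** The table stops at 4/58 = 6.9%, 10/116 = 8.6% and 17/174 = 9.8%. An observed rate above 14% would need more than 0.14 × 58 = 8.12, 0.14 × 116 = 16.24 and 0.14 × 174 = 24.36 events, that is 9, 17 and 25. The two statements cannot both be the rule.

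**3. The denominator at the milestone.** Untreated men = accrual × lag: 10 × 1.5 = 15 for a 45-day lag and 10 × 3 = 30 for 90 days. Applying the largest passing counts to the treated men only:

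| Milestone | 45-day lag | U | 90-day lag | U |
|---|---|---|---|---|
| 58 | 3 of 43 | 17.1% | 3 of 28 | 25.4% |
| 116 | 9 of 101 | 15.0% | 9 of 86 | 17.6% |
| 174 | 16 of 159 | 14.9% | 16 of 144 | 16.4% |

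Every limit is above 14%, though each count passes. These limits correct only for untreated men. They still assume that treated men have shown all their toxicity. Even with no lag, men enrolled in the last 3 months have under 90 days of follow-up, which leaves 58 − 30 = 28 of the first 58 with that much.

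**4. What continued counting would do.** If each treated group were followed until its full five-year toxicity had been counted, the probability of crossing 4/58, 10/116 or 17/174 (exact sequential binomial) is:

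- true rate 9%: 0.778 at the first group, plus 0.045, plus 0.009 = 0.832;
- true rate 14%: 0.970 + 0.020 + 0.004 = 0.994.

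The 9% result follows from the expected count: 0.09 × 58 = 5.2 events in the first group, against a boundary of 4. The 83% is a limiting case, reached only with complete follow-up. With 178 in the third row, the 9% figure moves by 0.3 points.

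**The case against.** The strongest reply is that this is a rule for stopping and does not certify safety. Nothing in the protocol says a passed milestone clears the treatment. The test of the toxicity rate against 9% plus 5 points is the upper limit in 11.4.1. The independent board meets quarterly, sees adverse events of all grades and can recommend termination at any count (12.3). It may also have set a counting convention at its first meeting. All of this stands and keeps the point minor. It does not rescue the 95% sentence in 12.5, which claims more than an enrolment-based count can deliver.

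A second reply is that 232 is described in 11.3 as a number of treated subjects, while 253 is the number to enrol, so the milestones may have been meant for treated men. That is plausible, but 12.5 says enrolled and 6.2 defines the term.

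A third is that the table rows can be read as patient groups that go on being counted. This matters for the size. Take a true 14% five-year rate, with half the toxicity in the first 3 months after treatment, the rest spread evenly to month 60, and a lag of 0 to 3 months. The chance of stopping is then about 5% to 43% if each count is frozen at its milestone. It is about 85% to 87% if each group is counted to month 29, the planned end of accrual.

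A reader might therefore infer that the rule is unlikely to detect a 14% rate. The documents do not support that, because they give neither the toxicity timing nor the counting convention, and the worst lag case needs every man to use all 90 days. Nor do they show that a 9/17/25 rule was ever meant: the sentence may only introduce the 14% threshold, and the table governs.

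**Conclusion.** The concern holds in three limited parts.

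- **Third row:** an error, 178 for 174. As printed it is one event stricter than the stated criterion.
- **Threshold sentence:** it conflicts with the table and should refer to the true rate.
- **95% requirement:** it is not met by staying below a boundary if the count is read at the enrolment milestone. At the first milestone the upper limit for a passing count is 17.1% with a 45-day lag and 25.4% with the full 90 days, at the planned 10 per month.

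The third part is conditional on the milestone reading, which the wording favours but does not settle. Whether men withdrawn for T3 disease stay in the denominator is also unstated; they would add to the problem, but no number is available.

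A reader might go further and infer that the counts 4, 10 and 17 are miscalculated, or that patients in this trial were left unprotected. Neither follows: the counts are exact for 58, 116 and 174, and the board's review does not depend on them. Severity is minor, and the 260 subjects in 11.2 suggest that the milestones have passed.

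**What to change.** 1. Change 178 to 174 in the third row.
2. Say that a true rate above 14% is too high, and that the counts come from an exact one-sided 95% binomial limit.
3. Apply the counts to the first 58, 116 and 174 treated patients. Keep counting grade 3-5 events in each group whenever they occur, and stop as soon as a count is reached.
4. State that staying below a boundary gives no 95% assurance on the five-year rate, which rests on 11.4.1.
5. Print the stopping probability at true rates of 9% and 14% (up to 83% and 99% with complete counting), and have the safety board confirm or revise the counts in that light.

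A 90-day window is an option for the board and not a required change. It would avoid most false stops only by ignoring late grade 3-5 events. With the printed counts and a true five-year rate of 14%, it would stop about 62% of the time if half the toxicity is early (7%), and about 30% if one third is.

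The cost is one paragraph and one table row with board agreement, and no extra patients or procedures. If the milestones have passed, what remains is a short record of how patients were counted at each one, with no 95% claim drawn from them.
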